5.3 Other variables

The following other variables are documented in this clinical trial:

- Demographics and other baseline characteristics (documented at Visit 1; age, sex, height, weight, race, ethnicity, localization of injury).
- Check of contraception (at Visit 1).
- Medical history (at Visit 1).
- Concomitant medication (every visit).

5.4 Derived variables

Area under the curves, calculated using the trapezoidal rule [1], will be determined for POM VAS pain scores. For quantitative variables the absolute changes from baseline (Visit 1) will also be determined.

5.5 Withdrawal/discontinuation

The study can be terminated at any time for any reason by the Sponsor, an IRB or a Health Authority. Such reasons may include, but are not limited to:

- change in the risk/benefit assessment due to unexpected findings related to the potential risk of the treatment,
- Detection of SUSARs that differ in severity, duration or frequency from the known safety profile
- Becoming aware of new evidence through publications or other clinical trials that would negatively impact the risk/benefit assessment

Should this be necessary, all patients should be seen as soon as possible and treated as described in Section 7 of CSP for a prematurely withdrawn patient. The Investigator may be informed of additional procedures to be followed in order to assure that adequate consideration is given to the protection of the patient's best interest.

The Investigator will be responsible for informing the IRB/REB/IEC of the early termination of the study. In the EU CRMB (EU legal representative) and Clinsearch will be responsible for notifying IECs, local authorities and the German Competent Authority, of the early termination

5.5.1 Schedule of assessments

The following table shows the Assessment Schedule of the clinical trial.

CRMB	Trial Substance:	Esflurbiprofen Hydrogel Patch	Study No.: EudraCT No.:	TK-254R-0201 2020-005165-14
	Short Title:	Local symptomatic and short-term treatment of pain in acute strains, sprains or bruises of the extremities following blunt trauma		KU SEIYAKU CO LTD.

Randomization	V2	V3	V4	V5	V6	Final visit ³ (V7)
	1 08 2	2	2	1	5	7, 8 or 9
-		-	-		•	7d (± 1d)
	$1211(\pm 1)$	2411 (±2)	4011 (±4)	72II (±4)	90II(±4)	$7a (\pm 1a)$
						X
X						X
Х	Х	Х	Х	X	Х	x
Х	х	х	х	X	Х	X
х						х
	х	х	х	х	х	х
		х	х	х	х	х
х	х	х	х	х	х	х
х						
х					х	
					х	х
х		х	х	х	х	
х						
	х	х	х	х	х	х
	х	х	х	х	х	x
	х	х	х	х	х	х
	х	х	х	x	х	x
			х	х		x
						x
					х	
	X X X X X X X X X X X X X X X X X X X	1 1 or 2 0h 12h (±1) x x <tr< td="">I I or 2 2 0h $12h (\pm 1)$ $24h (\pm 2)$ x x x x x x x x x x	I I or 2 2 3 0h $12h (\pm 1)$ $24h (\pm 2)$ $48h (\pm 4)$ x x x x x x x x x x x x x x x x x x x x x x x x x x x x x x x x x x x x x x x x x x x x x x x x x x x x x x x x x x x x x x x x x x	I I or 2 2 3 4 0h $12h (\pm 1)$ $24h (\pm 2)$ $48h (\pm 4)$ $72h (\pm 4)$ x x x x x x x X X X X X x X X X X X x X X X X X x X X X X X x X X X X X x X X X X X x X X X X X x X X X X X x X X X X X	I I or 2 2 3 4 5 0h 12h (±1) 24h (±2) 48h (±4) 72h (±4) 96h(±4) x x x x	</tr<>	I I or 2 2 0h $12h (\pm 1)$ $24h (\pm 2)$ x x x x x x x x x x	I I or 2 2 3 0h $12h (\pm 1)$ $24h (\pm 2)$ $48h (\pm 4)$ x x x x x x x x x x x x x x x x x x x x x x x x x x x x x x x x x x x x x x x x x x x x x x x x x x x x x x x x x x x x x x x x x x	I I or 2 2 3 4 0h $12h (\pm 1)$ $24h (\pm 2)$ $48h (\pm 4)$ $72h (\pm 4)$ x x x x x x x X X X X X x X X X X X x X X X X X x X X X X X x X X X X X x X X X X X x X X X X X x X X X X X x X X X X X	I I or 2 2 3 4 5 0h 12h (±1) 24h (±2) 48h (±4) 72h (±4) 96h(±4) x x x x

¹Female patients only; ²Patients will be given pouch containing IMP to take home in case of need to replace a detached patch. Patients bring IMP with them to each subsequent clinic visit. Patient apply patches themselves at 120h and 144h. ³A final visit will be conducted on all patients, including cases of early termination or withdrawal of consent.

CRMB	Trial Substance:	Esflurbiprofen Hydrogel Patch	Study No.: EudraCT No.:	TK-254R-0201 2020-005165-14
	Short Title:	Local symptomatic and short-term treatment of pain in acute strains, sprains or bruises of the extremities following blunt trauma		OKU SEIYAKU CO LTD.

6 SAMPLE SIZE

The calculation of 90 per treatment group is based on the following assumptions and considerations:

- Primary efficacy outcome is the change from baseline for POM at 72 hours after initiating treatment.
- Two-sided t-test situation with $\alpha = 5\%$.
- Assuming SD = 20 mm, the sample size provides approximately 80% power to detect a difference of 10 mm between two treatment groups if 64 patients per group are analysed.
- However, the sample size will be stipulated to n=90 per group in order to power also the two subgroup comparisons.
- Moreover, the sample size will be a total of 200 patients because a dropout-rate of approximately 10 % is taken into account.

7 DATA ENTRY AND VALIDATION

The data entry of all records documented in the CRFs is carried out by two independent data entry persons and result in two different data sets, which will be compared. Trial Master File will be corrected until conformity is proved. Furthermore, the data will be analyzed for completeness and several plausibility checks will be carried out (see Chapter 10).

8 COMPUTER SYSTEMS, SOFTWARE, AND VALIDATION OF PROGRAMS

8.1 Hardware

Used Hardware at CRMB is:

- Network servers:
- TERRA SERVER 6530 G3, 946 GB SSD, 16 GB Ram.
- Desktops (workstations): 6 Desktops based on AMD and Intel
- Scanners: F-Secure Antivirus 7.0 for Windows Server ESET NOD 32 Antivirus Version 9 is used on the desktops
- Backup method: Continous backup using VEEM.
 On every Friday a full backup with Acronis True Image echo for Windows server is performed (system and data). For the rest of the week a differential backup is created. The backups are stored on internal (RAID 5) and external hard discs.

8.2 Software

Used Software at CRMB is:

- DMSys from Sigmasoft, Version 5.1,
- SAS Version 9.4,
- Windows Server 2019 Network servers,
- Windows 10 on Workstations,
- Microsoft Office 2019 and Adobe Professional for reports, tracking of CRFs.

CRMB	Trial Substance:	Esflurbiprofen Hydrogel Patch	Study No.: TK-254R-0201 EudraCT No.: 2020-005165-14
	Short Title:	Local symptomatic and short-term treatment of pain in acute strains, sprains or bruises of the extremities following blunt trauma	Sponsor: TEIKOKU SEIYAKU CO LTD.

The data management is performed using the validated Data Management System DMSys, Version 5.1, and the statistical analysis is performed using the validated statistical analysis program SAS, Version 9.4 under Windows 10.

8.3 Validation of programs

All SAS programs start with a header in which the following information is contained:

- Name of the program,
- author,
- date of creation,
- used analysis DATA sets.

All tables, graphics and listings contain in footer the name of the program with which they were created, and the date of creation.

All formats will be filed in a permanent format catalogue.

All SAS programs will be checked by a second SAS programmer responsible for the quality control (QC). He/she will also check all LOG files for ERROR messages and WARNINGS. ERRORs must not occur. WARNINGs must be checked as to whether they lead to wrong results. Furthermore, the SAS programmer responsible for the QC will check the tables, figures, and listing for completeness and consistency. The review will be documented on the Program Validation Form.

The biometrician responsible for evaluation will make sure that the specifications of planned analysis have been correctly converted in SAS programs.

8.4 Restitution of programs

All SAS programs used in the analysis as well as the OUTPUT (listings, tables) will be stored, and archived together with the source code of the programs at CRM Biometrics GmbH.

9 CODING

Concomitant medications will be coded by means of the Drug Dictionary (WHO-DD, June 2021). Adverse events and diseases will be coded using MedDRA (Version 24.0), respectively.

10 DATA CHECKS

Before starting the statistical analysis, plausibility checks will be performed. A detailed list of edit checks can be found in the Data Management Plan (DMP, Appendix 5).

11 QUERIES

After performing the plausibility checks and the comparisons of the two data entry databases, the errors of the data entry will be corrected. Queries/Data Clarification Forms will be generated in the case of inconsistencies or missing data in the CRF. According to the resolved queries, changes of the data will be performed in the Master file, if necessary. In the case of remaining

CRMB	Trial Substance:	Esflurbiprofen Hydrogel Patch	Study No.: EudraCT No.:	TK-254R-0201 2020-005165-14
	Short Title:	Local symptomatic and short-term treatment of pain in acute strains, sprains or bruises of the extremities following blunt trauma		DKU SEIYAKU CO LTD.

unsolved queries, the Principal Investigator, the responsible statistician, the medical advisor and the project manager will decide how to handle these data and all decisions taken will be documented in detail.

12 BLIND REVIEW

A blind review meeting will take place before unblinding the randomization code. Any potential factors that could lead to unblinding of the study will be considered before this review. A listing of all protocol deviations with the proposed classification into minor and major protocol deviations and a list of all data irregularities or unresolved queries and a proposal for how the data are to be handled in the analysis, if necessary, will be provided in the Blind Review Meeting. At least the responsible biometrician and the Clinical Project Manager will sign the Blind Review protocol.

13 DATABASE CLOSURE

After all queries have been replied, the master file will be corrected, if necessary, and the decisions regarding the handling of the unresolved queries will be made, and the database will be closed.

14 STATISTICAL EVALUATION

14.1 General

All statistical analyses will be performed in accordance with the ICH E9 guideline.

14.2 Analysis populations

The following analysis populations will be used for analysis of study data:

Safety population: The safety population will include all randomized patients who received at least one dose of the IMP. Safety (e.g., AEs) will be analyzed in this population.

Full Analysis Set (FAS): The Full Analysis Set (FAS) will be all randomized patients who received at least one dose of IMP. The FAS population will be primary for the analysis of efficacy. Any exclusions from the FAS population will be made and documented before unblinding (e.g. never used IMP, ankle is not sprained, randomized twice). The Intention to treat (ITT) population is identical to the Full Analysis Set (FAS).

Per protocol (PP) population: The Per protocol (PP) population will include all patients who are randomized to the clinical trial, satisfy all of the inclusion/exclusion criteria, receive the correct IMP (as randomized), have efficacy data at the 72 hours assessment, with an adhesion score of 0, 1, 2, have taken no pain medication and have no other major protocol violations as defined during a blinded review meeting.

Moreover, the PP population for the adhesion analysis (PP-PA) will include all TDS except those that were intentionally removed early in the study (e.g. because of unacceptable irritation) or those that were on patients who discontinued use of the TDS before the end of the labeled duration of wear for reasons unrelated to adhesion (e.g. because of a protocol violation). The exclusions from the PP-PA population will be described in detail in the CSR. All exclusions will be discussed in the Blind Review Meeting before DBL.

CRMB	Trial Substance:	Esflurbiprofen Hydrogel Patch	Study No.: EudraCT No.:	TK-254R-0201 2020-005165-14
	Short Title:	Local symptomatic and short-term treatment of pain in acute strains, sprains or bruises of the extremities following blunt trauma	Sponsor: TEIKC	DKU SEIYAKU CO LTD.

Only the outcomes regarding primary and secondary efficacy variables will be analyzed using this clinical trial population.

Before the study is unblinded, each actual post-baseline visit will be mapped to the target visit time to which it is chronologically closest. This corresponds to the following visit windows: Visit 2 (Hours 12), Visit 3 (Hours 22-24), Visit 4 (Hours 44-52), Visit 5 (Hours 68-76), Visit 6 (Hours 92-100), Visit 7 (Hours 168+). The numbering of the actual visits (from Visit 1 to Visit 7) will then be changed as needed to improve the correspondence of the actual visit times to the protocol-specified schedule. Final determinations will also be made and documented before the study is unblinded to address visits that are equidistant to two nominal visit times (Hours 12, 24, 48, 72, 96, 168) or any other irregularities.

Before the study is unblinded, the timing of the diary assessments will be reviewed, and assessments will be reclassified into time slots as appropriate to ensure that all assessments in a given comparison were made a comparable amount of time after start of treatment.

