6.5.9 Study drug discontinuation and premature patient withdrawal

The study drug must be discontinued and the patient withdrawn from the study if the Investigator determines that continuing it would result in a significant safety risk for that patient. The following circumstances require study drug discontinuation:

- □ Withdrawal of informed consent
- □ Pregnancy
- □ Emergence of any clinically relevant serious adverse events
- Any other protocol deviation that results in a significant risk to the patient's safety

In addition to these requirements for study drug discontinuation, the Investigator should discontinue study drug for a given patient if, on balance, he/she thinks that continuation would be detrimental to the patient's well-being.

Patients may voluntarily withdraw from the study for any reason at any time. They may be considered withdrawn if they state an intention to withdraw, or fail to return for visits, or become lost to follow up for any other reason. If premature withdrawal occurs for any reason, the Investigator must determine the primary reason for a patient's premature withdrawal from the study and this information must be recorded on the Study Completion CRF.

Patients who are prematurely withdrawn from the study will not be replaced.

If a patient is discontinued or decides to withdraw from the study, all evaluations scheduled for the final visit will be performed within one week of study drug discontinuation. Every effort must be made to collect all the required data at the time of patient discontinuation. The Investigator or designee must complete the Study Drug Discontinuation, giving the date and primary reason for stopping the study drug.

For patients who are lost to follow-up (i.e. those patients whose status is unclear because they fail to appear for study visits without stating an intention to withdraw), the Investigator or designee should show "due diligence" by documenting in the source documents the steps taken to contact the patient, e.g. dates of telephone calls, registered letters, etc., in order to establish the reason for discontinuation and to check presence of any AEs.

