Teikoku Chemical Co. Ltd Clinical Study Protocol : TK-254R-0201

Documentation of use of rescue medication, if needed (diary check).

- \square Record changes in the use of concomitant medication (section 6.5.6).
- \square Record information on AEs (section 8.1).
- \Box Spontaneous pain intensity, pain at rest (PAR) (section 7.5.1)
- \Box Injury site pain-on-movement (POM) (section 7.5.1).
- □ Visit 4: Global efficacy assessments (GEA) by patient and investigator (section 7.5.1).
- \Box Adhesive power of patch (section 7.5.1).
- □ Local tolerability assessment (except V2).

Visit 5 (72h \pm 4 h)

- \Box Apply next dose of study medication.
- □ Count used/unused patches & collect used patches.
- □ Check for last intake of rescue medication no later than 6 hours prior to Visit.
- □ Documentation of use of rescue medication
- \square Record changes in the use of concomitant medication (section 6.5.6).
- \square Record information on AEs (section 8.1).
- □ Spontaneous pain intensity, pain at rest (PAR) (section 7.5.1)
- \Box Injury site pain-on-movement (POM) (section 7.5.1).
- \Box Global efficacy assessments (GEA) by patient and investigator (section 7.5.1).
- Responder rate 1 (number of patients achieving 50% reduction from baseline in the VAS score for POM)
- \Box Adhesive power of patch (section 7.5.1).
- □ Local tolerability assessment.

Visit 6 (96h+4h)

- □ Apply next dose of study medication.
- □ Count used/unused patches and collect used patches.
- \Box Use of rescue medication.
- \square Record changes in the use of concomitant medication (section 6.5.6).
- \square Record information on AEs (section 8.1).
- \Box Spontaneous pain intensity, pain at rest (PAR) (section 7.5.1).
- \Box Injury site pain-on-movement (POM) (section 7.5.1).

- \Box Adhesive power of patch (section 7.5.1).
- □ Local tolerability assessment.
- □ Dispense patient card (section 6.5.7) and diary (section 6.5.8) and instruct patient about appropriate use.
- Dispense three patches to the patient.
- \Box The patient is instructed on the method and time of application of study drug (section 6.5.4).

Visit 7 (Day 8 ± 2 days) - Final visit

Procedures for this visit are also to be completed if the patient terminates the study prematurely.

- \Box Count used/unused patches and collect used patches.
- \square Record changes in the use of concomitant medication (section 6.5.6).
- \Box Record information on AEs (section 8.1).

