9.4 Populations for analysis

- Full Analysis Set The Full Analysis Set will be all randomized patients who received at least one dose of study drug. The FAS population will be primary population for the analysis of efficacy. Any exclusions from the FAS population will be made and documented before unblinding (e.g. never used study medication, randomized twice). Additional secondary populations may be defined before unblinding and will be described in detail in the SAP.
- Safety Set The safety set (SAF) will include all randomized patients who received at least one dose of the study drug. Safety will be analyzed in this population.

Before the study is unblinded, each actual post-baseline visit will be mapped to the target visit time to which it is chronologically closest. This corresponds to the following visit windows: Visit 2 (Hours 12), Visit 3 (Hours 22-24), Visit 4 (Hours 44-52), Visit 5 (Hours 68-76), Visit 6 (Hours 92-100), Visit 7 (Hours 168+). The numbering of the actual visits (from Visit 1 to Visit 7) will then be changed as needed to improve the correspondence of the actual visit times to the protocol-specified schedule. Final determinations will also be made and documented before the study is unblinded to address visits that are equidistant to two nominal visit times (Hours 12, 24, 48, 72, 96, 168) or any other irregularities.

Before the study is unblinded, the timing of the diary assessments will be reviewed, and assessments will be reclassified into time slots as appropriate to ensure that all assessments in a given comparison were made a comparable amount of time after start of treatment.

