14.4.2 Secondary efficacy variables

- POM at injured site in mm measured using a 100 mm VAS at 12, 24, 48, 72, 96 and 168 hours after commencement of study treatment and will additionally presented by subgroup (table and Figure).
- AUC over time during first 12, 24, 48, 72, 96 and 168 hours for POM measured using a VAS; ordinate = POM score in mm, abscissa = time after treatment
- Pain-at-rest (PAR) at injured site in mm measured using a 100 mm VAS at 12, 24, 48 72, 96 and 168 hours.
- Reduction in VAS for POM from baseline:
- Time to meaningful reduction (30%)
- Time to optimal reduction (50%)
- Time to complete resolution of pain
- Responder rate 1 (defined as the proportion of patients achieving ≥50% reduction from baseline in the VAS score for POM at 72 hours)
- Responder rate 2 (defined as the proportion of patients able to resume training / normal physical activity by 168 hours)
- Clinical global assessment of efficacy as judged by investigator and patient at 48, 72 and 168 hours
- Overall dose of rescue medication needed (paracetamol).

Statistical test results for secondary variables will only be interpreted exploratorily.

Other important secondary efficacy outcomes are pain-on-movement on VAS at 12, 24, 48, 72, 96 and 168 hours after initiating treatment in the FAS population. These will be analyzed with an analysis-of-covariance (ANCOVA) model and center and subgroup as main effects. All other continuous efficacy outcomes will be analyzed based on the same model (excluding the baseline covariate when there is no appropriate baseline).

Differences between treatments on ordinal outcomes will be tested with Wilcoxon, stratified by center and subgroup.

Figures will show the time course of outcomes by treatment group for key quantitative outcomes. The primary outcome will also be summarized by center (if there is evidence of a treatment-by-center interaction), sex, age and race but without formal statistical comparisons of treatments.

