14.8 Missing data

- If assessments at any visit for Visits 2 (12 h) through Visit 6 (96 h) are missing, they will be imputed as the average of the preceding and the following assessments. Fractional values will be rounded down (including ordered categorical assessments). If assessment at Visit 7 is missing, the last observation will be carried forward.
- If a patient terminates prematurely,
 - all subsequent visits will be imputed by carrying the last non-missing observation forward.
 - for an adverse event suspected to be study-drug-related, then all subsequent visits will be imputed by carrying the baseline observation forward.
 - for lack of efficacy, all subsequent assessments will be imputed as the worst of all documented assessments.
 - for lack of efficacy or for an adverse event suspected to be study-drug-related and does not complete the global assessment of treatment satisfaction, it will be assigned the worst possible score.

CRMB	Trial Substance:	Esflurbiprofen Hydrogel Patch	Study No.: EudraCT No.:	TK-254R-0201 2020-005165-14
	Short Title:	Local symptomatic and short-term treatment of pain in acute strains, sprains or bruises of the extremities following blunt trauma	Sponsor: TEIKO	KU SEIYAKU CO LTD.

- If a patient discontinues for any other reason, missing global assessments at Visit
 7 will be imputed by LOCF from Visit 5 and missing assessments at Visit 5 will not be imputed.
- If a patient assesses efficacy at the site < 6 hours after using rescue medication, imputation will be discussed in the Blind Review Meeting, with consideration given to the frequency of this issue in the database and the elapsed time between rescue and assessment of efficacy.
- If a patient assesses spontaneous pain intensity and spontaneous pain relief at the time of rescue taken because of blunt trauma pain, any assessment conducted in the following 6 h will be replaced by the corresponding assessment done at the time of rescue.
- If a patient assesses spontaneous pain intensity and spontaneous pain relief at the time of rescue taken for reason other than blunt trauma pain, any assessment conducted in the following 6 h will be imputed as if the assessment were missed.
- If there are no assessments in the 12-24 h window, or the 24-48 h window,
 - if the patient has not prematurely terminated, a value from the last preceding assessment or assessment window will be carried forward.

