15 VISIT WINDOWS

All data will be organized and analyzed according to the scheduled visits outlined in the protocol.

Visit	1	2	3	4	5	6	7
Day	1	1 or 2	2	3	4	5	7, 8 or 9
Time after 1 st treatment	0 h	12 h (±1 h)	24 h (±2 h)	48 h (±4 h)	72 h (±4 h)	96 h (±4 h)	7 d (±1 d)

CRMB	Trial Substance:	Esflurbiprofen Hydrogel Patch	Study No.: TK-254R-0201 EudraCT No.: 2020-005165-14		
	Short Title:	Local symptomatic and short-term treatment of pain in acute strains, sprains or bruises of the extremities following blunt trauma	Sponsor: TEIKOKU SEIYAKU CO LTD.		

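### The hour list in SAP 14.2 is not the closest-target mapping it is said to express, and it omits on-schedule times for Visits 2, 3 and early Visit 7

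*SAP*

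**What the plan says.** SAP 14.2 and Protocol 9.4 carry the same text. Each actual post-baseline visit is to be "mapped to the target visit time to which it is chronologically closest". The next sentence presents a list of hours as the equivalent of that rule: "This corresponds to the following visit windows: Visit 2 (Hours 12), Visit 3 (Hours 22-24), Visit 4 (Hours 44-52", followed by 68-76 h for Visit 5, 92-100 h for Visit 6 and 168 h or later for Visit 7. Visits are then renumbered where needed. Decisions are to be made and documented before unblinding on "visits that are equidistant to two nominal visit times (Hours 12, 24, 48, 72, 96, 168) or any other irregularities".

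SAP 15 is headed as the section on visit windows. It says "All data will be organized and analyzed according to the scheduled visits outlined in the protocol" and tabulates the scheduled tolerances: 12 h ±1 h, 24 h ±2 h, 48, 72 and 96 h each ±4 h, and 7 d ±1 d. It does not say how these tolerances relate to the mapping in 14.2.

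**The concern.** The rule and the list sit in adjacent sentences and are declared equivalent, but they give different assignments. Suppose a programmer codes the list. A Visit 3 held at 25 h or a Visit 7 held at 150 h, both on schedule, then falls in no window. So does a Visit 5 held at 80 h, which the rule assigns to 72 h. An unassigned score could then be treated as missing and filled under SAP 14.8, by averaging neighbouring visits or, at Visit 7, by carrying the last value forward.

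The outcomes exposed are pain on movement and pain at rest at 12, 24 and 168 h, and the AUC and SPID values that use them. For the primary outcome only visits outside the 72 h ±4 h schedule are exposed.

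**Working it through.** **Inputs.** Targets of 12, 24, 48, 72, 96 and 168 h and the listed windows come from SAP 14.2. Tolerances come from SAP 15. The alternative Visit 7 tolerance of ±2 days comes from Protocol Table 7-1.

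**Step 1: try to reproduce the list from the rule.** Under a closest-target rule the boundary between two adjacent targets is their midpoint:

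- (12 + 24)/2 = 18 h
- (24 + 48)/2 = 36 h
- (48 + 72)/2 = 60 h
- (72 + 96)/2 = 84 h
- (96 + 168)/2 = 132 h

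If baseline (0 h) is also counted as a target, Visit 2 starts at (0 + 12)/2 = 6 h and nothing else changes.

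**Step 2: compare list, rule and schedule (hours).**

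| Visit | Listed | Closest rule | Scheduled | List = rule? | List = schedule? |
|---|---|---|---|---|---|
| 2 | 12 | up to 18 | 11-13 | no | no |
| 3 | 22-24 | 18-36 | 22-26 | no | no |
| 4 | 44-52 | 36-60 | 44-52 | no | yes |
| 5 | 68-76 | 60-84 | 68-76 | no | yes |
| 6 | 92-100 | 84-132 | 92-100 | no | yes |
| 7 | 168 or later | 132 or later | 144-192 (±1 d) or 120-216 (±2 d) | no | no |

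The list matches the rule for 0 of 6 visits and the schedule for 3 of 6. The rule leaves no gaps. The list leaves 12-22, 24-44, 52-68, 76-92 and 100-168 h unassigned.

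**Step 3: permitted time that the list omits.**

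- Visit 2: all of 11-13 h except the 12 h point. If the entry means 12 h rounded to the nearest hour (11.5-12.5 h, my assumption), 1 of 2 h is omitted.
- Visit 3: 26 − 24 = 2 of 4 h.
- Visit 7: 168 − 144 = 24 of 48 h under ±1 d, or 168 − 120 = 48 of 96 h under ±2 d. At the late end the list has no limit, whereas the schedule stops at 192 or 216 h.
- Visits 4 to 6: none.

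These are widths of time, not shares of visits. The documents contain no visit-time data.

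**Step 4: the primary time point.** Visit 5 spans 76 − 68 = 8 h in the list and 84 − 60 = 24 h under the rule. The two disagree only at 60-68 h and 76-84 h, both outside the scheduled 72 h ±4 h.

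**Step 5: which reading does the text favour?** The rule covers every visit. The provision for equidistant visits has work to do only under the rule, because none of the five midpoints lies in a listed window. SAP 15 also organises data by scheduled visit. With the ±1 d tolerance, every scheduled range lies inside its closest-target window. With ±2 d there is one exception: a Visit 7 at 120 to under 132 h would be nearest to 96 h and map to Visit 6.

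**The case against.** The best defence is that the closest-target rule is clear and workable, and that the list only illustrates it. No passage sets an observed out-of-window score to missing. The blinded review can settle irregular visits, and SAP 14.4.2 says: "Statistical test results for secondary variables will only be interpreted exploratorily". Most of this stands and keeps the point small. It does not rescue the sentence. The list is offered as the rule's equivalent, appears in both documents, and is wrong for every visit. The provision for irregularities deals with individual unusual visits; it does not tell a programmer which of two general statements to code.

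Three stronger readings are tempting, and the documents do not support them.

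- A reader might infer that on-schedule data will be lost, or that the primary analysis is compromised. Loss requires the list to be coded in preference to the rule, and on-schedule Visit 5 values are identical under both.
- A reader might see a conflict for withdrawn patients. Protocol 6.5.9 says "all evaluations scheduled for the final visit will be performed within one week of study drug discontinuation", and such an evaluation at 60-84 h would map to Visit 5, while SAP 14.8 says that after premature termination "all subsequent visits will be imputed by carrying the last non-missing observation forward". The Protocol glossary defines termination as the later of the final evaluation visit and the stop of study drug. On that definition the evaluation is not after termination, which largely removes the conflict.
- A reader might take the participation period in SAP 2, seven days plus one, as a further Visit 7 tolerance. It describes length of participation: Day 1 to Day 8 inclusive is eight days.

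**Conclusion.** The point holds: the declared equivalence is false for all six windows. The list is narrower than the schedule for Visits 2 and 3. For Visit 7 it cuts off the early half of the scheduled window and leaves the late end open, so it is not simply narrower there. The practical effect is limited to the 12, 24 and 168 h scores and the measures derived from them, and to primary values from visits at 60-68 or 76-84 h. It arises only if the list is followed. How many visits are concerned cannot be stated from the documents.

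This assumes that the listed hours are elapsed time from first treatment, and that SPID, for which the SAP gives no formula, uses the POM scores at the scheduled visits.

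A separate, minor point is that the Visit 7 tolerance is inconsistent. Protocol Table 4-1 and SAP 3 put ±24 h beside Day 8 ±2 days. Protocol 6.5.8 and the Visit 7 entry in Protocol section 7 give ±2 days. Protocol Table 7-1 gives ±2 d beside Day 7, 8 or 9. SAP 5.5.1 and SAP 15 give ±1 d. The list would be wrong under any of these, but the passages must be reconciled.

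**What to change.** Make these changes in the SAP before unblinding:

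1. In 14.2, replace the hour list with the windows that the stated rule implies: Visit 2 up to 18 h, Visit 3 18-36 h, Visit 4 36-60 h, Visit 5 60-84 h, Visit 6 84-132 h, Visit 7 132 h and later. Leave exact midpoints, and two visits that map to the same target, to the existing provision for blinded decisions.
2. In SAP 15, state that the tolerances are scheduled times for judging deviations, not analysis cut-offs.
3. Note in the SAP that the same list in Protocol 9.4 is read as the closest-target rule.
4. Separately, reconcile the Visit 7 tolerance within the SAP's own text (sections 3, 5.5.1 and 15). Changing the protocol passages would need a written amendment under Protocol 11.1.

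Items 1 to 3 cost a few sentences. SAP 1 says the SAP is finalised after the blind review meeting, so there is an occasion to make them. The only downside is that some off-schedule values stay with their nearest visit, which the stated rule already implies.
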